10.1 Allocation of AEs

For AE reporting, the allocation of an AE in the different treatment phases is shown in [Table 10-1](#).

If not otherwise specified (see below specific safety evaluation), all AEs with start date before final visit and SAEs within 30 days after final visit will be included in the AE analyses.

Table 10-1 Allocation of AEs

Screening (V1)	V101 or V102 – V103 (val run-in)	V103 – V199 (LCZ run-in)	V201(Ran d) – CMP	CMP – CMP + 30d (SAE only)	Phase AE to be reported in
X					Reported by the site from Informed Consent
	X				Report AE in valsartan run-in
		X			Report AE in LCZ696 run-in
			X		Report AE in DB
	X	X2			Report as two separate AEs: One with onset date X for valsartan run-in and one with onset date X2 for LCZ696 run-in
	(X)	X	X2		Report as two separate AEs:

Screening (V1)	V101 or V102 – V103 (val run-in)	V103 – V199 (LCZ run-in)	V201(Rand) – CMP	CMP – CMP + 30d (SAE only)	Phase AE to be reported in
			X, X2		One with onset date X (X) for LCZ696 (valsartan) run-in and one with onset date X2 for DB Report as one AE: One with onset date X for DB
	(X)	X	X		Report AE with onset date X (X) in LCZ696 (valsartan) run-in
	(X)	(X)	X	X (SAE) X2 (SAE)	Report SAE in the 30 days follow-up Report as two separate AEs: One AE with onset date X (X) for DB (valsartan or LCZ696 run-in) and one SAE with onset date X2 for the 30 days follow-up

X and (X) stands for onset and possible onset date of AE, respectively.

X2 stands for same AE but with an increased severity.

10.2 Analysis for the identified and potential risks in the risk management plan

The identified and potential risks for LCZ696 are listed in [Table 10-2](#). Besides the specifically specified analyses for each risk, which are listed in the table, the following standard analysis will be applied to all risks.

- Incidence (absolute and relative frequency) rates in terms of patient regardless of study drug relationship by treatment group
- Exposure adjusted incidence rates per 100 patient years regardless of study drug relationship, by treatment
- Listing of subject numbers per risk.

The search paths for the related preferred terms (PTs), high level group term (HLGT), high level term (HLT), in Standard Medical Queries (SMQs), or NMQ in MedDRA for the risks in [Table 10-2](#) are store in the [LCZ696 Case Retrieval Strategy \(2019\)](#).

Table 10-2 Identified and potential risks

Risks	Analysis
Hyperkalemia	
 1. Frequency of hyperkalemia leading to treatment interruption and discontinuation regardless of study drug relationship, by treatment 2. Categorical analysis with frequency and percentage by treatment for patients with serum potassium ≥ 5.5 mEq/L, >6.0 mEq/L and >6.5 mEq/L by treatment.
Hypotension	
 1. Blood pressure summary (mean, standard deviation, median, and range) including measurement at each visit and change from baseline will be provided by treatment 2. Summary with frequency and percentage by treatment for patients with: 
 a. systolic blood pressure (SBP) <100 mmHg; b. 30 mmHg drop in SBP;

Risks	Analysis
Angioedema Renal impairment	
c. simultaneous SBP <100 mmHg and 30 mmHg drop in systolic BP.
 
Frequency and percentage by treatment (Standard statistical analysis)
 
 1. Summary for serum creatinine and eGFR by treatment 2. Summary for frequency and percentage by treatment for patients with: 
 a. eGFR decline by >25%, >40%, >50%, and >30 mL/min/1.73 m²; b. Serum creatinine increase by >50%; c. Serum creatinine level >0.5 mg/dL, >2.0 mg/dL, >2.5 mg/dL, >3.0 mg/dL 3. Subgroup analyses on the relationship between eGFR < 60 and ≥60 mL/min/1.73 m² at baseline and incidence rate/severity of AEs/laboratory parameters indicating newly occurred/worsening of renal impairment.
Hypersensitivity	Standard analysis
Anaphylaxis/anaphylactoid reactions	Standard analysis
Hepatotoxicity	
 1. Summary with frequency and percentage by treatment for patients with: 
 a. ALT or AST >3x ULN; b. ALT or AST >5x ULN; c. ALT or AST >8x ULN; d. ALT or AST >10x ULN; e. ALT or AST >20x ULN; f. ALT or AST >3x ULN and TB >1.5x ULN; g. ALT or AST >3x ULN and TB >2x ULN; h. ALT or AST >5x ULN and TB >2x ULN; i. ALT or AST >8x ULN and TB >2x ULN; j. ALT or AST >10x ULN and TB >2x ULN; k. ALT or AST >20x ULN and TB >2x ULN; l. ALP > 2 x ULN m. ALP > 3 x ULN n. ALP > 5 x ULN o. TB > 1.5 x ULN p. TB > 2 x ULN q. TB > 3 x ULN r. ALP > 3x ULN and total bilirubin > 2x ULN s. ALP > 5x ULN and total bilirubin > 2x ULN t. ALT or AST > 3x ULN and total bilirubin > 2x ULN and ALP =< 2x ULN u. (ALT or AST > 3x ULN and total bilirubin > 2x ULN and ALP =< 2x ULN) or reported Hy's Law case v. ALT or AST > 3x ULN and (nausea or vomiting or fatigue or general malaise or abdominal pain or (rash and eosinophilia)) w. TB >3x ULN and AST or ALT are ≤3 x ULN and alkaline phosphatase ≤1.5x ULN; x. AP >3x ULN and AST, ALT, TB are within normal range.

Risks	Analysis
	2. A cross-tabulation of baseline and worst post-baseline values by below, within and above normal range categories will be provided. Shift tables will be provided for the parameters AST, ALT, TB and AP.
Embryo-fetal toxicity/Lethality	Standard analysis
Neonatal/infantile toxicity through exposure from breast milk	Standard analysis
Statin drug-drug interaction	Standard analysis for patients who take statin during randomized treatment epoch (at baseline and post-baseline)
Malignancy	Standard analysis
Cognitive impairment	Standard analysis

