6.5.7 Angioedema

Angioedema is a type of abrupt swelling that occurs under the skin and/or mucous membranes and is often localized to the head, neck, throat, and/or tongue, but may occur elsewhere, including the genitalia and intestines. Severe cases may be associated with airway compromise.

It is important that the investigator pays special attention to any swelling or edema that may resemble angioedema or angioedema-like events that may be reported by patients. If such an event occurs, the investigator will complete an Adjudication Questionnaire for an Angioedema-like Event form (provided by Novartis) to summarize the event, its treatment, and its ultimate outcome. This report along with the requisite medical documentation must be submitted to Novartis as soon as possible. Follow-up reports must be communicated to Novartis as soon as new information regarding the event becomes available. All hospital records related to the event must be communicated to Novartis.

The investigator may be also be contacted by Novartis regarding AEs that may resemble an angioedema-like event. A list of terms that are considered “angioedema-like” (e.g., periorbital swelling) will be provided to sites in a manual. The investigator or his/her delegated staff must complete the required forms and provide the required medical records for all such events, regardless of whether the investigator views the event in question as angioedema or not.

All angioedema reports will be forwarded to an Angioedema Adjudication Committee by Novartis for assessment.

Information regarding this committee is outlined in [Section 8.5](#). Details on the procedures for reporting angioedema events will be provided to investigators in a manual.

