8.5 Adjudication Committees

Clinical Endpoint Committee

All events, which could potentially fulfill the criteria for the primary, secondary, or other endpoints will be assessed during the study and reported to the Clinical Endpoint Committee (CEC) for adjudication.

The CEC will be responsible for classifying all death events and for determining whether pre-specified endpoint criteria were met for the non-fatal events. Sites are instructed to take a conservative approach when reporting endpoints; if the investigator suspects an endpoint may

have occurred, it should report the event to the CEC for the final determination. The membership and responsibilities of the CEC Committee will be defined in a separate document provided to the sites. This document will include definitions for endpoints and guidelines on the endpoint reporting process.

Angioedema Adjudication Committee

If an angioedema or angioedema-like event occurs, the investigator will complete an Adjudication Questionnaire for an Angioedema-like Event form (provided by Novartis). Details on the process of reporting angioedema and angioedema like events are outlined in a manual provided to investigators.

Submission of an angioedema report is not a substitution for the submission of an SAE report. If an angioedema-like event satisfies the definition of an SAE, the investigator must submit an SAE report in addition to the Adjudication Questionnaire for an Angioedema-like Event.

The membership and responsibilities of the Angioedema Adjudication Committee are defined in a separate document that will be provided to the sites.

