9.5.3 Safety variables

The safety and tolerability assessments are listed below:

- Identified and potential risks
- AEs and SAEs
- Sitting systolic, diastolic BP, and pulse pressure
- Heart rate
- Symptomatic hypotension
- Angioedema
- Hyperkalemia
- Renal dysfunction
- Other relevant laboratory values
- ECG changes

The assessment of safety will be based primarily on the frequency of AEs, SAEs, and laboratory abnormalities. Other safety data will be summarized as appropriate.

The incidence of treatment-emergent AEs (new or worsened) will be summarized by primary system organ class, preferred term, severity, and relationship to study drug. In addition, the

incidence of death, SAEs, and AEs leading to discontinuation will be summarized separately by primary system organ class and preferred term.

The incidence of AEs related to the identified and potential risks will be summarized by SMQ preferred terms.

Laboratory data will be summarized by presenting shift tables using extended normal ranges (baseline to most extreme post-baseline value), by presenting summary statistics of raw data and change from baseline values (mean, medians, standard deviations, ranges) and by the flagging of notable values in data listings. LFT categorical analysis will also be provided.

Data from other tests (e.g., ECG or vital signs) will be listed, notable values will be flagged, and any other information collected will be listed as appropriate.

Safety analyses will be performed based on the safety set. There will be no formal statistical inference analysis.

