- Rate of change in eGFR (eGFR slope);
- Time from randomization to new onset diabetes mellitus (NODM);
- Time to new onset of atrial fibrillation (AF);
- Number of days staying in intensive care unit (ICU), number of stays in intensive care unit (ICU), number of re-hospitalizations for HF, and number of ER visits for HF;
- Indicator of 30 day HF rehospitalization (after a prior HF hospitalization during double blind phase);
- Number of rehospitalizations within 30 days after discharge;
- Time between HF hospital readmissions;
- Changes in pre-specified biomarkers (e.g., cardiac, vascular, renal, collagen, metabolism, and inflammatory biomarkers) from baseline to predefined time-points (in a subset of patients);
- Variables to characterize the PK of valsartan, AHU377, and LBQ657 at steady-state in patients receiving LCZ696 using population modeling and/or non-compartmental based methods;
- Change from baseline in Mini-Mental State Examination (MMSE) summary score at year 2 (week 96).

Among the variables above, some of them or their components need to be adjudicated to confirm the reported types and occurrences based on the unified criteria for analyses. The adjudication of these events is based on an adjudication process through an independent Endpoint Adjudication Committee. The following events will be assessed by the Endpoint Adjudication Committee during the study:

- All death events;
- Unplanned hospitalization for HF;
- MI;
- Stroke;
- Renal dysfunction (including occurrence of end stage renal disease);
- Others (new onset atrial fibrillation (NOAF), NODM)

In the analysis, as specified before, only adjudicated events will be utilized if the events included in the analysis are required to be adjudicated. However, in the sensitivity analysis, the investigator reported events may also be used.

As specified before, all events and endpoints occurred or measured prior to or at the specified analysis time-points (such as Month 8, Month 12, etc.), including the analysis cut-off date, will be counted, unless otherwise specified.

Censoring variables:

Number of events and time-to-event variable are usually subject to censoring. The censoring can be caused by withdrawal of consent, lost to follow-up, other competing events, or administrative reasons (interim or analysis cutoff date). Below are the rules for deriving censoring variables in the analyses (primary, secondary, exploratory):

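### The SAP counts angioedema from MedDRA search terms and reported adverse events, and no analysis uses the Angioedema Adjudication Committee's verdict

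*SAP*

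**What the plan says.** **Collection.** Protocol 8.5 states: "If an angioedema or angioedema-like event occurs, the investigator will complete an Adjudication Questionnaire for an Angioedema-like Event form". Protocol 6.5.7 requires forms and medical records for all events on a list of angioedema-like terms, periorbital swelling being the example given, "regardless of whether the investigator views the event in question as angioedema or not". It then says: "All angioedema reports will be forwarded to an Angioedema Adjudication Committee by Novartis for assessment".

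**Analysis.** The SAP analyzes angioedema in two places. In 10.2, Table 10-2, the entry is "Frequency and percentage by treatment (Standard statistical analysis)". Cases for all risks in that table are found by queries: "The search paths for the related preferred terms (PTs), high level group term (HLGT), high level term (HLT)" and the related SMQ and NMQ paths are kept in the LCZ696 Case Retrieval Strategy (2019), a separate file. In 10.3, angioedema is one of five adverse events of interest to be summarized separately. Protocol 9.5.3 takes the same line: "The incidence of AEs related to the identified and potential risks will be summarized by SMQ preferred terms".

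**Adjudication in the SAP.** SAP 9.2 introduces its list with "The following events will be assessed by the Endpoint Adjudication Committee during the study". The list covers deaths, HF hospitalization, MI, stroke, renal dysfunction, new onset AF and new onset diabetes. Angioedema is not on it, and the SAP does not name the angioedema committee.

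**The concern.** Collection is deliberately over-inclusive: sites submit anything that resembles angioedema, and the committee decides what is. That decision restores specificity, yet it feeds no planned table. The count a reader will take as the trial's angioedema result comes from a different filter, namely how a reported term was coded and whether the code falls inside the query.

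The protocol gives angioedema particular weight. Section 1.1 recalls the increased incidence with an earlier vasopeptidase inhibitor and explains why LCZ696 is expected to differ. Prior angioedema is an exclusion (4.2), an episode in run-in ends participation (3.1), and a suspected case later requires permanent discontinuation of study drug (5.5.9). Exclusion and run-in should leave few true cases after randomization, so a handful of misclassified ones could change the picture. If the SAP does not say which count leads, the choice between the reported and the adjudicated count could be made after both are known.

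**Working it through.** **1. Does any SAP rule bring the committee's verdict in?** The nearest candidate is the statement in SAP 9.2 that only adjudicated events are used where adjudication is required. It stands in the efficacy chapter, opens by referring to the variables listed just above it, and belongs to the Endpoint Adjudication Committee's list. The safety chapter has its own counting rule: SAP 10.1 and 10.3 include all AEs up to the final visit and SAEs up to 30 days after it, with no mention of adjudication. Elsewhere the SAP says so when it wants confirmed events: 9.1 for primary and secondary events, 9.3.3.1 for new onset AF, 9.3.3.3 for the clinical composite. For angioedema it does not.

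**2. What is already planned?** SAP 10.2 applies incidence, exposure-adjusted rates per 100 patient-years and a listing of subject numbers to every risk. SAP 10 evaluates the two run-in phases and the double-blind phase separately, and 10.3 adds preferred-term tables and annualized run-in rates. So the summaries exist; what is missing is their application to confirmed cases.

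**3. Which way can the count err?** It can include events the committee rejected. It can also miss confirmed cases coded outside the query. If the query finds the same fraction of confirmed cases in both arms, the ratio is unchanged and the counts shrink. If it adds unrelated swelling at the same rate in both arms, the ratio moves toward 1.

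**4. Illustration of the added-swelling case.** The documents give no angioedema rate, power or margin, so there is no figure to reproduce and every rate below is an assumption. Inputs: 4,600 patients (Protocol 4) randomized 1:1 (Protocol 5.2), so 2,300 per arm; p is the true rate and b the proportion with unrelated swelling caught by the query.

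Counted rate = p + b(1 − p).

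With p = 0.6% on LCZ696, 0.2% on valsartan and b = 1%:

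- LCZ696: 0.006 + 0.01 × 0.994 = 0.01594, and × 2,300 ≈ 37 patients
- Valsartan: 0.002 + 0.01 × 0.998 = 0.01198, and × 2,300 ≈ 28 patients
- Ratio: 0.01594 / 0.01198 = 1.33
- Share of counted cases that are real: 0.008 / 0.02792 = 29%

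| Assumed true rates (LCZ696 vs valsartan) | b = 0 | b = 0.5% | b = 1% | b = 2% |
|---|---|---|---|---|
| 0.6% vs 0.2% | 3.00 | 1.57 | 1.33 | 1.18 |
| 0.4% vs 0.2% | 2.00 | 1.28 | 1.17 | 1.09 |
| 0.5% vs 0.1% | 5.00 | 1.66 | 1.36 | 1.19 |

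Entries are ratios of counted rates. The difference in counted rates barely changes: for 0.6% vs 0.2% it is 0.4 percentage points × (1 − b), about 9 patients in 2,300 throughout. The effect falls on the ratio and on the absolute level in each arm.

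**The case against.** The strongest reply is that dilution needs a broad query, and the query cannot be seen. The Case Retrieval Strategy may be narrow, in which case b is near zero. The wide net in Protocol 6.5.7 governs what sites submit to the committee; it does not define the SAP's search. This stands.

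It is also fair that the SAP gives a reader several ways to look behind the headline. Preferred-term tables separate angioedema terms from other edema terms, and the subject listing lets cases be traced. Exposure-adjusted and phase-specific rates are already there. An inclusive count of reported events is a defensible safety default, since adjudication can reject true cases, and Protocol 1.1 describes the rate to date as low and similar to comparators. These points limit the harm, and they are why the MedDRA count should stay.

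A reader might infer more: that non-specific edema will overwhelm the angioedema signal, with Protocol Table 7-1 as evidence because it lists generalized and peripheral edema as common. The documents do not support that. Table 7-1 sets which events are exempt from SUSAR unblinding, and nothing routes those terms into the angioedema search. Nor do they support an argument from lost power: Protocol 9.5.3 plans no formal inference for safety, and neither document plans a relative-risk test of angioedema.

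What the reply does not remove is the gap itself. Even a narrow query counts coded reports, not committee-confirmed cases.

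**Conclusion.** The point holds as a mismatch between what is collected and what is analyzed. The protocol requires adjudication of every angioedema-like event; the SAP states a different case-finding method and gives the verdict no analysis. The lead angioedema count is therefore unadjudicated and may err in either direction.

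Its size is unknown. Under the assumed rates, unrelated swelling caught in 1% to 2% of each arm would bring a true ratio of 3.00 down to between 1.33 and 1.18; with none caught there is no dilution. These figures rest on invented rates, on equal background swelling in both arms, and on a query whose breadth is not documented. They show a possibility only. The conclusion about the missing analysis rests on the text alone and needs none of them. It does not touch the efficacy analyses; it is worth correcting because the verdicts are already being gathered.

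**What to change.** In SAP 10.2 (Table 10-2, Angioedema) and 10.3:

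- Make committee-confirmed angioedema the main angioedema table, using the incidence, exposure-adjusted rate and phase-specific summaries already planned.
- Show the committee's classification, and submitted against confirmed events by arm.
- Keep the MedDRA-query count as the supporting table.

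State this before treatment codes are opened, so that the lead count is not chosen with both results in view.

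The cost is one extra table set from data the protocol already has collected. The confirmed table will probably hold fewer events and give wider intervals, and adjudication may reject some true cases; the supporting count covers both.

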4.1 Inclusion criteria

Patients eligible for inclusion in this study have to fulfill **all** of the following criteria:

1. Written informed consent must be obtained before any assessment is performed.
2. ≥ 50 years of age, male or female.
3. LVEF $\geq 45\%$ by echo during the screening epoch, or within 6 months prior to Visit 1 (any local LVEF measurement made using echo only).
4. Symptom(s) of HF requiring treatment with diuretic(s) for at least 30 days prior to Visit 1.
5. Current symptom(s) of HF (NYHA class II-IV) at Visit 1.
6. Structural heart disease evidenced by at least one of the following echo findings (any local measurement made during the screening epoch or within the 6 months prior to Visit 1):

- a. left atrial (LA) enlargement defined by at least one of the following: LA width (diameter) ≥ 3.8 cm **or** LA length ≥ 5.0 cm **or** LA area ≥ 20 cm² or LA volume ≥ 55 mL **or** LA volume index ≥ 29 mL/m²
 - b. left ventricular hypertrophy (LVH) defined by septal thickness or posterior wall thickness ≥ 1.1 cm
7. Patients with at least one of the following:
- a. a HF hospitalization (defined as HF as the major reason for hospitalization) within 9 months prior to Visit 1 **and** NT-proBNP >200 pg/ml for patients not in AF or >600 pg/ml for patients in AF on Visit 1 ECG, **OR**
 - b. NT-proBNP >300 pg/ml for patients not in AF or >900 pg/ml for patients in AF on the Visit 1 ECG.

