 - d. SBP $<$ 100 mmHg or symptomatic hypotension as determined by the investigator at Visit 103 or Visit 199/201
11. Patients with history of any dilated cardiomyopathy, including peripartum cardiomyopathy, chemotherapy induced cardiomyopathy, or viral myocarditis.
 12. Evidence of right sided HF in the absence of left-sided structural heart disease.
 13. Known pericardial constriction, genetic hypertrophic cardiomyopathy, or infiltrative cardiomyopathy.
 14. Clinically significant congenital heart disease that could be the cause of the patient's symptoms and signs of HF.
 15. Presence of hemodynamically significant valvular heart disease in the opinion of the investigator.
 16. Stroke, transient ischemic attack, carotid surgery or carotid angioplasty within the 3 months prior to Visit 1.
 17. Coronary or carotid artery disease or valvular heart disease likely to require surgical or percutaneous intervention during the trial.
 18. Life-threatening or uncontrolled dysrhythmia, including symptomatic or sustained ventricular tachycardia and atrial fibrillation or flutter with a resting ventricular rate $>$ 110 beats per minute (bpm).
 19. Patients with a cardiac resynchronization therapy (CRT) device.
 20. Patients with prior major organ transplant or intent to transplant (i.e. on transplant list).
 21. Any surgical or medical condition, which in the opinion of the investigator, may place the patient at higher risk from his/her participation in the study, or is likely to prevent the patient from complying with the requirements of the study or completing the study.
 22. Any surgical or medical condition which might significantly alter the absorption, distribution, metabolism, or excretion of study drugs, including but not limited to any of the following:
 - any history of pancreatic injury, pancreatitis or evidence of impaired pancreatic function/injury within the last 5 years
 23. Evidence of hepatic disease as determined by any one of the following: SGOT (AST) or SGPT (ALT) values exceeding 3x the upper limit of normal (ULN), bilirubin $>$ 1.5 mg/dl at Visit 1.
 24. Patients with one of the following:
 - a. eGFR $<$ 30 mL/min/1.73m² as calculated by the Modification in Diet in Renal Disease (MDRD) formula at Visit 1, **or**
 - b. eGFR $<$ 25 mL/min/1.73m² at Visit 103 or Visit 199/201, **or**
 - c. eGFR reduction $>$ 35% (compared to Visit 1) at Visit 103 or Visit 199/201

25. Presence of known functionally significant bilateral renal artery stenosis

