6.5.4.2 Clinical chemistry

Blood urea nitrogen (BUN), creatinine, total bilirubin, fractionated bilirubin (if total bilirubin >2x ULN), AST, ALT, alkaline phosphatase, sodium, glucose (plasma), hemoglobin

A1C, lipid profile, potassium, chloride, calcium, total protein, albumin, and uric acid will be measured. Potassium, BUN and creatinine will be obtained at study visits where abbreviated laboratory evaluations are scheduled.

6.5.4.3 eGFR

Estimated eGFR will be calculated by the central or local laboratory using the following MDRD formula (Stevens et al 2006):

Estimated GFR (mL/min/1.73 m²) = 175 × (standardized S_{Cr} in mg/dL)^{-1.154} × (age in years)^{-0.203} × (0.742 if female) × (1.212 if black), where S_{Cr} is the standardized serum creatinine value.

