- c. If hypotension persists, the study drug should be down-titrated or even temporarily withdrawn. The dose re-challenge and medications adjust guidelines described in [Section 5.5.5](#) should be adhered to as much as possible.

17 Appendix 5: Guidelines for the management of renal dysfunction

General principles:

Glomerular filtration rate in HF patients depends on intrinsic renal function and on a balance between afferent and efferent glomerular arterial tonicity. This tonicity is partly regulated by a stimulation of angiotensin II and could be affected by either study drug. Moreover, renal dysfunction may develop or may deteriorate in some patients after study drug administration. These recommendations have been developed to guide the investigators in managing patients with renal dysfunction after randomization.

Two types of response to serum creatinine increase are described:

Surveillance situation

If, at any time after randomization, eGFR decreases by $\geq 25\%$ from baseline (Visit 1) (or if serum creatinine concentration increase to 2.5 mg/dL [221 $\mu\text{mol/L}$]), the investigator will check for potentially reversible causes of renal dysfunction such as:

- Non-steroidal anti-inflammatory drug intake, antibiotics, or other treatments known to affect creatinine
- Volume decrease, including that resulting from excessive dosing of diuretics
- Urinary infection
- Urinary tract obstruction
- Study drug

Action situation

If a patient's eGFR decreases by $\geq 40\%$ from baseline (Visit 1) (or if serum creatinine concentration rises above 3 mg/dL (265 $\mu\text{mol/L}$)), the investigator will check for potentially reversible causes of renal dysfunction (see above).

The investigator may consider down-titration of study drug. If the investigator judges that study drug has to be stopped, he/she will have to contact the Novartis medical monitor or his/her designee. Thereafter, serum creatinine assessments will have to be repeated at least

each week until levels return to acceptable values. If study drug was stopped, every effort will be done to restart it again, according to clinical conditions.

18 Appendix 6: Blood log for PK sample collection

Visit	Visit name	Timepoint	Volume	Sample Number	Dose reference ID
199	Treatment run in	Predose	2 mL	1	1
203 ^a	Week 16	0 hours pre-dose	2 ml	2	2
203 ^b	Week 16	0.5 - 2 hours post-dose	2 ml	3	2
203 ^c	Week 16	3-5 hours post-dose	2 ml	4	2
205 ^a	Week 48	0 hours pre-dose	2 ml	5	3

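### The first creatinine entry in the SAP's renal-impairment summary, a level above 0.5 mg/dL, is met by nearly every patient at baseline and cannot contrast the arms

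*SAP*

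**What the plan says.** SAP Section 10.2, Table 10-2, lists what will be tabulated for renal impairment. Item 2 is introduced as "Summary for frequency and percentage by treatment for patients with" certain findings, and has three parts:

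- 2a is a change in eGFR: "eGFR decline by >25%, >40%, >50"%, plus an absolute fall of more than 30 mL/min/1.73 m2.
- 2b is a change in creatinine: "Serum creatinine increase by >50"%.
- 2c is a creatinine level: "Serum creatinine level >0.5 mg/dL, >2.0 mg/dL, >2.5 mg/dL, >3.0 mg/dL".

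Nothing in Table 10-2 limits 2c to patients who were at or below the threshold at baseline. Elsewhere, Protocol Appendix 5 uses creatinine levels of 2.5 and 3 mg/dL as triggers (for surveillance, "serum creatinine concentration increase to 2.5 mg/dL"). Neither document uses 0.5 mg/dL as a level anywhere else.

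**The concern.** The four thresholds in 2c share one noun, level, but they do not belong together. Levels of 2.0, 2.5 and 3.0 mg/dL mark reduced kidney function. A level of 0.5 mg/dL is one that an older heart-failure patient with ordinary kidney function already exceeds. An entry that almost everyone meets before randomized treatment starts cannot show whether either drug worsens renal function. Programmed literally, the safety table would carry a line near 100% in both arms. If a rise of 0.5 mg/dL was meant, that rise would have no line of its own.

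**Working it through.** **Inputs.** The eGFR formula is in Protocol Section 6.5.4.3: 175 × Scr^(-1.154) × age^(-0.203), with the multipliers "0.742 if female) × (1.212 if black), where S" being serum creatinine in mg/dL. The population is at least "50 years of age, male or female" (Protocol Section 4.1). The renal entry limit excludes eGFR below 30 mL/min/1.73 m2 "as calculated by the Modification in Diet in Renal Disease (MDRD) formula at Visit 1" (Protocol Section 4.2), and there is no upper limit. The plan states no figure to reproduce. As a unit check, the factor 88.4 in SAP Section 10.4.1 gives 2.5 × 88.4 = 221 and 3 × 88.4 = 265.2 µmol/L, in line with Protocol Appendix 5.

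**Step 1: eGFR needed to stay at or below 0.5 mg/dL.** For a non-black man aged 70: 175 × 0.5^(-1.154) × 70^(-0.203) = 164.4. For a non-black woman: 164.4 × 0.742 = 122.0. All strata (mL/min/1.73 m2):

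| Age | Men, non-black | Women, non-black | Men, black | Women, black |
|---|---|---|---|---|
| 50 | 176.0 | 130.6 | 213.3 | 158.3 |
| 70 | 164.4 | 122.0 | 199.2 | 147.8 |
| 80 | 160.0 | 118.7 | 193.9 | 143.9 |
| 90 | 156.2 | 115.9 | 189.3 | 140.5 |

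Without the race factor the range at ages 50 to 80 is 119 to 176. With it, the top of the range is 213.

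**Step 2: the formula inverted.** Scr = [eGFR / (175 × age^(-0.203) × multipliers)]^(-1/1.154). Across ages 50 to 90, both sexes and both race terms, creatinine is 0.62 to 1.06 mg/dL at eGFR 90, 0.88 to 1.50 at eGFR 60, and 1.61 to 2.74 at the entry limit of 30. All of these are above 0.5.

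**Step 3: share of patients above each threshold at baseline.** The documents give no baseline distribution, so these are assumptions: eGFR normal and truncated below 30; age mean 72, SD 9, limited to 50 to 95; 50% women; 3% black.

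| Assumed eGFR mean/SD | Above 0.5 mg/dL | Above 2.0 mg/dL | Median creatinine |
|---|---|---|---|
| 55/15 | 100.0% | 1.41% | 1.13 |
| 60/20 | 99.94% | 1.32% | 1.04 |
| 65/20 | 99.87% | 0.86% | 0.98 |
| 75/25 | 98.34% | 0.63% | 0.87 |
| 90/25 (implausibly healthy) | 94.73% | 0.18% | 0.75 |

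At most 0.01% exceed 2.5 mg/dL and about none exceed 3.0. Those thresholds start near zero and leave room for a difference between arms. The 0.5 mg/dL entry does not.

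**Step 4: could the baseline-exclusion rule rescue it?** SAP Section 10.4.1 removes patients already abnormal at baseline, but for Table 10-3. Section 10.4.2 cites Table 10-3 for the renal data although the renal item is in Table 10-2, so someone might borrow that rule. With it, only about 0% to 5% of patients would stay in the denominator for the 0.5 mg/dL entry.

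**Step 5: what a rise above 0.5 mg/dL would add.** A 50% increase equals 0.5 mg/dL at a baseline of 1.0. Above 1.0, item 2b misses a rise just over 0.5. A 25% eGFR fall needs a creatinine ratio of 0.75^(-1/1.154) = 1.283, so such a rise also escapes the 25% eGFR item when baseline exceeds 0.5/0.283 ≈ 1.77 mg/dL. Patients in that range are eligible (step 2).

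**The case against.** The strongest reply is that little is lost. Creatinine worsening is also captured by item 2b, by the eGFR declines in 2a, by the creatinine and eGFR summaries, by the change-from-baseline and shift tables in SAP Section 10.4.1, and by the separate renal adverse-event summaries in Section 10.3. Step 5 can also be turned round. From a baseline of 1.77 to 2.0 mg/dL, a rise above 0.5 ends above 2.27 and so crosses 2.0; from 2.0 to 2.5 it crosses 2.5; from 2.5 to 3.0 it crosses 3.0. Most such patients would therefore appear somewhere in item 2. Protocol Section 9.5.3 also plans no formal inference on safety. All of this stands, and it limits the point to one descriptive entry. It does not make that entry informative.

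Three stronger readings are tempting and are not supported:

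- **That the whole creatinine line, or the renal safety assessment, is empty.** Three of the four thresholds in 2c can discriminate, and 2a and 2b are unaffected.
- **That the documents show a rise was intended.** Items 2a and 2b are changes, which makes it plausible, but no passage says so.
- **That the 136.8 µmol/L creatinine cut-off in SAP Table 10-3 (136.8/88.4 = 1.55 mg/dL) is a related error.** It matches no other creatinine cut-off, but the notable-value tables differ from Table 10-2 elsewhere too. Potassium is above 5.0 and at least 6.0 mmol/L in Table 10-3, against at least 5.5, above 6.0 and above 6.5 mEq/L in Table 10-2. Systolic pressure is below 90 mmHg with a fall of more than 20 in Table 10-4, against below 100 in Table 10-2. A difference alone does not show a mistake.

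**Conclusion.** The point holds for the 0.5 mg/dL entry only. Read literally it is a level, and the documents' own formula and entry criteria put nearly all patients above it at baseline. The share is about 95% to 100% under the assumed eGFR distributions, and at least 98% if the deliberately healthy scenario is set aside. That share rests on assumption; the eGFR of 119 or more needed to fall at or below the threshold at ages 50 to 80 does not. The consequence is minor: one descriptive safety category cannot contrast the arms, and a separate count of absolute rises, useful mainly when baseline creatinine is above 1.0 mg/dL, is missing. Efficacy results, alpha and sample size are untouched.

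**What to change.** Take 0.5 mg/dL out of item 2c and give it its own line as an increase in serum creatinine of more than 0.5 mg/dL from the double-blind baseline, in keeping with the change wording of 2a and 2b. The sponsor should confirm that this is the intended meaning. Keep 2.0, 2.5 and 3.0 mg/dL in 2c as levels. SAP Section 4 already sets the double-blind baseline for safety laboratory values at the randomization visit, and creatinine is already measured at follow-up, so no new data are needed. The cost is one table line and one derived indicator.
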